## **Data Safety Monitoring.**

### Data Safety Monitoring Plan

[name] will serve as our independent DSM. He is not directly involved in data collection or patient interaction and will be used to avoid conflict of interest. The DSM will be unblinded, so that he can identify any alarming trends in adverse events or serious adverse events that may warrant modification or stopping of the study. The independent DSM will conduct periodic unblinded assessments of the aggregate data at 25% (20 patients), 50% (39 patients), 75% (59 patients) and 100% (78 patients) study enrollment. If enrollment is slow, then the independent DSM will review all aggregate adverse events at least yearly and review completed electronic adverse event case report forms (stored in RedCAP) at least quarterly during throughout the year.

[name] will serve as the Clinical Monitor. The Clinical Monitor will review all adverse events as they occur to make sure that they fall within reason of the study (expected possible adverse events). The Clinical Monitor will contact the DSM if there are concerns regarding a greater than expected number of adverse events or serious adverse events. All serious adverse events will be reported to the DSM within 24 hours of identification of the event's occurrence. The DSM will review these events in an unblinded fashion. If there is an alarming trend with multiple occurrences of serious adverse events that are determined to be significant enough to warrant modification or stopping of the trial, then the DSM will notify the PI.

The study investigator-sponsor is responsible for ensuring that all adverse and unexpected events related to study participation are reported in a timely fashion to the FDA and institution IRB.

#### Self-audit

An internal self-auditing of the blinded data will be conducted by the PI and co-PI. The data evaluated by the PI and co-PI during self-audits will be in the blinded form. Subject groups will only be identified by the arbitrary letter assigned to them by the study pharmacist in order to protect the true identity of their group (placebo or Exparel®). An initial self-audit will be conducted after completion of the 1st patient participation. During this audit, the PI and co-PI will review and discuss:

- abnormal laboratory data
- cumulative pain scores
- cumulative opioid use
- secondary outcomes
- adverse events
- signed informed consents
- any need for revision of study methods and procedures or data collection forms

Also reviewed during self-audits will be any feedback from involved departments (including pharmacy, anesthesia and nursing) regarding adverse events or concerns related to the subjects' participation. These departments may contact the PI or co-PI with any concerns at any time during the study via telephone or email.

A repeat self-audit will be conducted after completion of the 3rd patient participation to evaluate effectiveness of any changes made to the study protocol and/or data collection forms. Another self-audit will occur following 50% completion of subject participation (39 patients).

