## II. CHARACTERISTICS OF THE RESEARCH POPULATION

### Number of subjects.

The study will include 78 patients, 39 patients in the study drug arm and 39 patients in the control arm. Since there are two primary outcomes, we set the type I error at 0.025 for the power analysis. Based on results from a prior study by Barr et al., we assumed a baseline Numerical Rating Scale (NRS) score for pain of 53.2 with standard deviation of 24.1 and a baseline cumulative morphine requirement over 24 hours of 23.2 mg with standard deviation of 8.3 mg. The proposed sample size was calculated to achieve 86% power to detect a 30% decrease in mean NRS scores at the 2.5% level of type I error (two-sided). This sample size also provides for a 98% power to detect a 30% decrease in total opioid consumption over the first 24 hours post-operatively. Note that we assumed the standard deviation decreases accordingly. A 5% drop out rate was included into the sample size calculation.

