### Randomization and Blinding

Patients will be randomized on the day of surgery to either placebo or treatment group. The subjects will be randomized in blocks of 4 to ensure a 1:1 ratio of placebo to treatment groups.

- Placebo: 0.9% normal saline
- Treatment group: 0.53% Exparel®

A randomization sheet will be generated by the study pharmacist, listing the randomization schedule in sequence for each block. The study pharmacist will have control of the randomization sheet. At the time of randomization, he will go to the next available row to determine which medication to dispense. The randomization sheet will document each subject's number, initials, date of surgery and study arm (active or placebo).

The study pharmacist will hold the key identifying which study group corresponds with which letter. In order to maintain blinding of the study investigators, the pharmacist will not reveal the subject's group assignment and data collection will be done according to the subject number. At quarterly intervals during the trial, the study pharmacist will reveal the blinding to the Independent Data/Safety Monitor (DSM) only. This will enable the Independent DSM to capture for any alarming trends in adverse events or serious adverse events as they are occurring. At completion of data collection and analysis for the entire study, the pharmacist will provide the study investigators with a copy of the report revealing which subject belonged to which study group.

The subjects will be blinded to their study arm and remain blinded for the entire duration of this study. Subjects who wish to know which drug they received (Exparel® or placebo), may contact the PI or co-PI and they will be informed of their study group following completion the study.

The study investigators, surgeon administering the medications, operating room staff and ICU/floor staff will all remain blinded. Only the pharmacist who will prepare and dispense the medication will be unblinded.

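### The self-audit's group-letter rule leaves the PI and co-PI free to see the treatment contrast at 39 patients, so it does not by itself secure their blinding

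*Combined protocol and SAP*

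**What the plan says.** The Self-audit section of the combined protocol and SAP has the PI and co-PI review data that it describes as blinded, on the ground that "Subject groups will only be identified by the arbitrary letter assigned to them by the study pharmacist". Randomization and Blinding shows what the letter denotes: "The study pharmacist will hold the key identifying which study group corresponds with which letter". It is a code for the arm, not for the subject. The rule is written for self-audits in general. Audits follow the first and third patients, and then: "Another self-audit will occur following 50% completion of subject participation (39 patients").

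The listed content needs careful reading. A list that includes cumulative pain scores, cumulative opioid use and "any need for revision of study methods and procedures or data collection forms" is introduced for the first audit, when one patient has finished. The third-patient audit is meant to check whether any changes worked. The only content given for self-audits generally is input from pharmacy, anesthesia and nursing about adverse events or concerns. No efficacy content is stated for the audit at 39 patients, and tabulation by letter is neither described nor excluded.

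The blinding commitments are in Randomization and Blinding: "The study investigators, surgeon administering the medications, operating room staff and ICU/floor staff will all remain blinded"; "data collection will be done according to the subject number"; and assignments reach the investigators only at the end: "At completion of data collection and analysis for the entire study, the pharmacist will provide the study investigators with a copy of the report" showing each subject's arm. During the trial, allocation is disclosed to the independent DSM alone.

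**The concern.** A letter hides the name of an arm but not the difference between arms. Anyone who sees pain scores or opioid use split by letter sees the size of the interim difference. Since the trial expects Exparel to lower both, that person can also guess which letter is which. The Self-audit text says that the coding is there to protect the identity of the groups, and at 39 patients it may not do so.

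The potential viewers are the PI and co-PI, who under Data Storage and Confidentiality can export data and alter the collection forms. Some analysis choices are still open. Data Analysis lists six NRS AUC intervals and nine opioid intervals and names none as primary, although Number of subjects sizes opioid use on the first 24 hours. Statistical analysis adjusts for covariates that it does not name. It does partly settle the longitudinal method, since GEE or weighted GEE is preferred if it disagrees with the mixed model. Knowledge of the interim contrast while the interval and covariates are unnamed would weaken confidence in a later choice, even one made in good faith.

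**Working it through.** **Inputs (Number of subjects).** NRS control mean 53.2, SD 24.1. Opioid use over 24 hours, control mean 23.2 mg, SD 8.3 mg. Planned reduction 30%, so the differences are 0.30 × 53.2 = 15.96 and 0.30 × 23.2 = 6.96 mg. Two-sided alpha is 0.025 per outcome, with 39 per arm and 5% dropout. The plan adds: "Note that we assumed the standard deviation decreases accordingly". I read this as the SD falling in proportion to the mean, giving Exparel-arm SDs of 0.7 × 24.1 = 16.87 and 0.7 × 8.3 = 5.81. A mean of 53.2 cannot lie on the trial's 0-10 NRS, but only the ratio of difference to SD matters here.

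**Reproducing the plan's power (86% and 98%).** With 37 per arm after dropout and a normal approximation:
- NRS: SE = sqrt((24.1² + 16.87²)/37) = 4.836; z = 15.96/4.836 = 3.300; power = Φ(3.300 − 2.241) = 85.5%.
- Opioid: SE = sqrt((8.3² + 5.81²)/37) = 1.666; z = 6.96/1.666 = 4.179; power = Φ(4.179 − 2.241) = 97.4%.

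A t-test with 39 per arm gives 86.1% and 97.6%. Equal SDs give only 73.7% and 91.9%, so the proportional-SD reading is the one that fits.

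**The audit at 39 patients, if outcomes were viewed by letter.** With 1:1 allocation, take 19.5 per arm. For a fractional reduction r with control mean m and SD s:

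z = r·m / sqrt((s² + ((1 − r)·s)²)/19.5), and P(lower-mean letter is Exparel) = Φ(z).

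| True reduction | NRS | Opioid |
|---|---|---|
| 30% (planned) | 15.96/6.662, z = 2.396, P = 99.2% | 6.96/2.294, z = 3.034, P = 99.9% |
| 15% (assumed) | 7.98/7.163, z = 1.114, P = 87% | 3.48/2.467, z = 1.411, P = 92% |
| 10% (assumed) | 5.32/7.342, z = 0.725, P = 77% | 2.32/2.529, z = 0.917, P = 82% |
| None | z = 0, P = 50% | z = 0, P = 50% |

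A 20/19 or 19/20 split changes P by less than 0.001. The documents give no correlation between the outcomes. For an assumed correlation of 0 to 0.7, both point to Exparel with probability 99% (30% effect), 80-84% (15%) and 63-70% (10%).

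**Would the contrast look clear?** The chance of nominal two-sided p < 0.05 is Φ(z − 1.96) + Φ(−z − 1.96): 67% and 86% at the 30% effect (Welch t-test, 20 versus 19: 65% and 84%), 20% and 29% at 15%, and 11% and 15% at 10%.

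**Whose arms could be revealed?** At most the 39 audited patients, and only if the listing shows individual letters. Blocks are of 4 and 39 = 9 × 4 + 3. If the audited patients are the first 39 randomized, the listing is in randomization order and the block size is known, patient 40's letter also follows. Nothing extends this to patients 41-78: data are collected by subject number, Data Storage and Confidentiality lists no group letter among the stored items, and no self-audit is scheduled after 39.

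**The case against.** The strongest reply is that the plan does not describe the event these figures measure. The list naming the outcomes belongs to the one-patient audit, where no group contrast can exist. So does the item on revising methods. The general content is departmental feedback on safety, and the section can fairly be read as quality control of conduct. This stands. A reader might infer that the PI and co-PI are scheduled to compare efficacy by letter at 39 patients and then decide on changes to methods; the text does not support that.

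It can also be said that little turns on such knowledge. The audited patients' 72-hour outcomes are already recorded, ward staff are blinded, and no test or efficacy stopping rule is attached to the audit. This stands too, and limits the harm. The open analysis choices are a separate weakness that the fix would not cure. If the final comparison is itself run on coded groups, which is an inference, the contrast would be visible then as well.

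Finally, the 99% figures rest on the sponsor's own assumed effect. Even then, the NRS difference would miss nominal p < 0.05 in about a third of trials.

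None of this shows that the letter protects the blind. The letter rule covers all self-audits, and no section confines them to pooled data.

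**Conclusion.** The point holds as a gap in a safeguard. The letter rule permits, without requiring, a by-arm view of the primary outcomes at 39 patients, and so does not secure the commitment that investigators stay blinded until data collection and analysis are complete. Under the planning values with proportional SDs, such a view would almost certainly identify Exparel if the 30% effect is real. It would do so less reliably at an assumed 15% or 10%, and no better than chance with no effect. The size of the difference would be visible in every case.

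Two stronger readings are tempting and unsupported. One is that type I error is inflated: no test or efficacy decision is tied to the audit, so there is nothing to compute. The other is that the second half of the trial would be unblinded: decoding reaches the 39 audited patients at most, plus patient 40 under the conditions above. What remains is possible knowledge of interim results by the PI and co-PI while the primary interval and covariates are unnamed. That merits a cheap correction, not a redesign.

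**What to change.** In the Self-audit section, replace the sentence on letter coding with: *Self-audits will use pooled or individual-subject data without any group code; all by-arm review is left to the independent DSM.* Keep the other audit content as it is. Laboratory data, consents, forms, adverse events and completeness of outcomes can all be checked by subject number, and no audit task described needs the letter. Block size need not change, because removing the letter also closes the patient-40 route.

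The cost is one sentence and the absence of a letter field from the audit listing. The PI and co-PI lose any by-group view during the trial. By-arm safety oversight is kept, since the Data Safety Monitoring Plan already gives the DSM unblinded aggregate reviews at 20, 39, 59 and 78 patients.

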#### Indications for termination of study

The study will be terminated if an overwhelming amount of serious adverse events deemed related to therapy (e.g. significant new cardiac arrhythmias, CNS reactions, wound infection/dehiscence or severe allergic reactions) occur in either the Exparel® group or the placebo group.

#### **Data Storage and Confidentiality.**

Data collection will be entered and stored in the Research Electronic Data Capture (REDCap) system, which is a password-protected web application for building and managing online surveys and databases. REDCap allows database creation and storage of collected data in a secure manner. A comprehensive REDCap database will be created by the PI, co-PI and study coordinator. Only the PI and co-PI will have full administrative access to the database; meaning that they can add users, restrict levels of user access, export data and change data collection forms. The co-PI and trained study investigators will be in charge of entering patient data into the developed data collection forms. Each patient will be assigned a unique identification number (UID) upon initial entry into the REDCap database. Limited access to the REDCap database will be granted to the study statisticians and Medical/Safety Monitor. These persons will be allowed read-only access with all patient identifiers blocked (subjects identifiable only by their assigned UID). A printed key linking the patient medical record number (MRN) and UID, as well as any questionnaires including patient identifiers will be kept in a locked cabinet in [name] office. Only [name] and the co-PI will have access to the file. All printed data collection sheets will contain only the subject's UID.

The database will include data collection sheets that will store demographic information and clinical outcomes for each subject, including the following information: age at time of surgery, sex, race,

comorbidities (diabetes mellitus, COPD, smoker), left ventricular ejection fraction (%), baseline pain assessment score, surgical procedure performed, intraoperative measures (aortic cross-clamp time, LIMA harvest, cardiopulmonary bypass time, amount of crystalloid/blood products/cell saver received), total intraoperative opiate and benzodiazepines administered. Subjects' NVPS and NRS pain scores, opiate requirements, length of stay, time to first bowel movement and any adverse events will also be stored on data collection sheets.

At completion of data collection and entry into the database, all identifiers linking patient to UID will be destroyed and only the key will remain. The key will be destroyed following completion of this study. Study records will be maintained in a secured location for 3 years following closing of the study. No identifiers will be released in reported results or publications.

#### IV. RISK/BENEFIT ASSESSMENT

**Risk Category:** This study constitutes a greater than minimal risk to the patient.

Potential physical harm arises from the possible side effects of Exparel®. Neurologic and cardiac adverse reactions that have been reported with Exparel® administration include dizziness (6.2%), headache (3.8%), somnolence (2.1%), hypoesthesia (1.5%), lethargy (1.3%), tachycardia (3.9%) and bradycardia (1.6%). High levels of bupivacaine in the plasma result from accidental overdose, unintended intravascular injection or accumulation of the drug in the plasma secondary to decreased hepatic metabolic degradation or decreased plasma protein binding capacity due to acidosis. Clinical trials of Exparel® reveal a good safety profile. Side effects that have been reported in clinical trials are represented in the following table.

**Table 1: Adverse reactions reported with use of Exparel®**

Incidence	Adverse reaction
Most common (≥ 10%)	Nausea, constipation, vomiting
Common (≥ 2 or ≤ 10%)	Pyrexia, dizziness, peripheral edema, anemia, hypotension, pruritus, tachycardia, headache, insomnia, postoperative anemia, muscle spasm, hemorrhagic anemia, back pain, somnolence, procedural pain
Less common/rare (< 2%)	Chills, erythema, bradycardia, palpitations, supraventricular/ventricular extrasystoles, ventricular tachycardia, anxiety, urinary retention, pain, edema, tremor, postural dizziness, paresthesia, syncope, incision site edema, procedural hypertension/hypotension, procedural nausea, muscular weakness, neck pain, cold sweat, urticaria, confusional state, depression, agitation, hyperhidrosis, restlessness, blurred vision, tinnitus, hypoxia, apnea, urinary incontinence, drug hypersensitivity.

Information reproduced from: *Exparel Prescribing Information*. 23 Jan. 2012. Pacira Pharms, Inc. San Diego, CA.

All parasternal intercostal nerve blocks will be performed by a cardiac surgeon familiar with the study protocol and experienced in performing the procedure. The benefit of performing parasternal blocks prior to sternal closure is the ability to directly visualize and confirm appropriate placement of the needle tip. The syringe will be aspirated prior to injection to avoid intravascular injection of the drug. Hemodynamics and electrocardiography tracings will be monitored closely for arrhythmias and hypotension following administration of the drug.

PCA's are not routinely used after cardiac surgery, but are often used after other major surgeries including abdominal and orthopedic procedures. The risks of PCA are related to the adverse effects of opioid use, which may include: constipation, nausea/vomiting, sedation, respiratory depression, pruritus,

confusion/hallucination, urinary retention, sweating, miosis and myoclonic jerks. All patients will be monitored closely while using the PCA and if they start showing signs of opioid toxicity, then PCA dosing will be decreased or changed appropriately. If patients show signs of narcotic overdose (respiratory rate < 8 breaths per minute, over-sedation, or muscle rigidity), then naloxone will be administered for opioid reversal.

This study also constitutes a potential psychological stress arising from the blinding of subjects as to which research arm (placebo vs. Exparel®) they are assigned. There is also a risk of invasion of privacy because of the storage of identifiable clinical data. All clinical data will be in de-identified form. The key containing identifiers and linking medical record number will be kept secure and be accessible only to the PI and primary study coordinator. All clinical data released will be in de-identified form.

Potential benefits to the subjects are that the parasternal intercostal nerve blocks with Exparel® may provide improved pain control. This would benefit the patients by leading to less discomfort post-operatively, less narcotic requirements, lower morbidity and quicker time to recovery. Patients randomized to the placebo group would receive no direct benefit from participating in this study.

## **V. SUBJECT IDENTIFICATION, RECRUITMENT AND CONSENT/ASSENT**

Assessment for patient eligibility for the study will be performed by a qualified physician participating in the care of the patient who is familiar with the study and its objectives. Patients meeting eligibility criteria and none of the exclusion criteria will be recruited during their initial outpatient clinic visit prior to surgery.

Capacity of the individual will be ascertained by the research personnel obtaining consent. The study, risks and benefits of participation will be described to the subjects by the PI, co-investigators or study personnel. Determination of capacity is based upon the potential subject's ability to respond to the process appropriately. The person who obtains the consent will ensure that the subject is alert, able to communicate, able to understand information about the research, make a decision based upon the information and give informed consent. The research personnel obtaining consent will ask questions such as naming potential risks of participating in the study, summarizing the aim of the study, asking the subject to explain what he/she would do if he/she no longer wanted to participate, and asking the subject to explain what he/she would do if he/she experienced distress or discomfort during the study in order to assess the research subjects ability to comprehend and consent.

Willing participants will be presented with a detailed consent form explaining the purpose and nature of the study. The consent form will be in the appropriate language for the patient. Consents will be obtained by an authorized study investigator with the use of a language or sign language interpreter if necessary. The investigator obtaining consent will explain to the patient that participation is not required and that refusal to participate will not alter the quality of their care.

The consent form will be written in a language comprehensible by the lay public. Patients will be given adequate time to review the study with the surgeon and meet the PI if desired. All questions will be encouraged and answered. The consent form will contain contact information of the PI, participating surgeons, and primary study investigator who may be contacted if any further questions arise.

